1.16 RANDOMIZATION

Randomization for this study occurs at the site level. Sites will be randomized by the PM, to **Arm 1** (MiCAP with IF) or **Arm 2** (MiCAP with IF+EF) using the following steps.

Step 1: Data on site size (number of beneficiaries [patients]) and Clinical Quality Assessment Review (CQAR) scores will be obtained.

Step 2: We will block sites in pairs with similar size and CQAR scores, and flip a coin to determine **Arm 1** or **Arm 2** assignment for study.

The PM will maintain a confidential file documenting study Arm by site. Only the PI/PM will know Arm assignment by site.

1.17 STUDY PARTICIPATION

Voluntary study participation from sites, clinicians (RNs/OTs/SWs/IFs), and beneficiaries will occur.

Sites and clinicians will be informed of the benefits of CAPABLE from prior work; beneficiaries who received CAPABLE had improved ADL/IADLs, fewer falls and hospitalizations as well as being highly satisfied; and clinicians with increased knowledge in CAPABLE improved those beneficiaries outcomes.

Sites: PI/PM will contact a site via phone to confirm intent to participate; then provide the contract for review. Sites who sign a contract agree to be a part of the study.

Clinicians: PI will ask clinicians (RN, OT, and SW, IFs) to complete CAPABLE training using a flyer/email. Clinicians who sign the consent, agree to be a part of the study.

Beneficiaries: The state and sites will provide the Opt-out Consent document to the beneficiaries, which includes an option to opt out of the study by calling the PI, if desired.

1.18 INFORMED CONSENT AND HIPAA COMPLIANCE

Clinician Informed Consent Clinician (RN/OT/SW/IF) informed consent will be conducted and an electronic signature obtained on the consent form approved by IRB prior to data collection and CAPABLE training. The consent form will be modified and approved by the IRBs, if changes are necessary, prior to use.

Beneficiary Opt-out Consent and HIPAA (Health Insurance Portability and Accountability Act)

Authorization Alteration via a waiver of documentation of informed consent for the Medicaid beneficiaries will occur via two modes.

- For current Waiver beneficiaries: the State or sites will mail the Opt-out Consent document or the sites will hand deliver opt-out consent form to the beneficiary during the next home visit.
- For new Waiver beneficiaries: sites will include Opt-out Consent document in enrollment packets, which will be hand delivered to the beneficiary during their initial home visit in the Mi Choice program.

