1.3 SPECIFIC AIMS

The **specific aims** are as follows.

Aim A1 To test the effects of MiCAP with IF alone versus MiCAP with IF+EF with respect to the site-level outcomes of adoption and sustainability (**primary**) and beneficiary-level outcomes of ADL/IADLs, pain, depression, falls, emergency department (ED) visits and hospitalizations (**secondary**) over the next 12 months.

Aim A2 Mechanism-of-action To determine whether the effects of EF+IF versus IF on primary outcomes are mediated by clinician attitude or self-efficacy at 9 months.

Aim A3 To benchmark the effects of IF and EF+IF on beneficiary outcomes following implementation as compared to pre-intervention.

Exploratory Aim A4 To compare the primary and secondary outcomes within 12 months, potential mediators at 9 months, and baseline leadership and readiness for sites with SIC of >50% versus sites with SIC \leq 50% at 6 months in each arm.

Exploratory Aim A5 To explore whether baseline site leadership and readiness moderate the impact of EF+IF compared to IF on primary and secondary outcomes within 12 months in order to determine which sites may require facilitation that is more intensive.

Exploratory Aim A6 To evaluate clinician satisfaction at 1 month, and the cost of implementation and policy impact for IF and IF+EF at 12 months.

The National Institutes of Health (NIH) defines Implementation Science (IS) as the process of applying evidence to the treatment or prevention of human disease.¹⁹⁻²⁰ A scientific study of methods to promote uptake of evidence into routine care to improve quality and effectiveness of healthcare through the study of influences on clinician and organizational behavior.²¹ This study is significant because it addresses testing of multimodal implementation strategies of an evidence-based intervention (CAPABLE) in a Medicaid setting to improve the quality and effectiveness of a waiver.

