1.7 INCLUSION AND EXCLUSION CRITERIA

Inclusion Criteria

Included are waiver sites under contract as a waiver provider in MI who use the Center for Information Management (CIM) electronic health record (EHR); clinicians employed at the site who are trained in CAPABLE; and beneficiaries who receive care from a clinician trained in CAPABLE.

Exclusion Criteria

Sites not contracted as a waiver site or those not using CIM’s EHR will be excluded.

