1.9 ORGANIZATIONS ASSOCIATED WITH THE STUDY

NIA The National Institutes of Aging funded the project (NIA 1 R15 AG058193-01A1). As such, for this study, all requirements (i.e., privacy, confidentiality, Health Insurance Portability and Accountability Act (HIPAA), IRB, budget, report, dissemination, data sharing, protocol, etc.) will be met through execution and implementation of the Notice of Award (NOA) agreement with the university.

CMS The Center for Medicare and Medicaid Services is the oversight organization of MDHHS. As such, for this study, all requirements (i.e., privacy, confidentiality, HIPAA, etc.) will be met through execution and implementation of the MDHHS IRB and DUA.

MDHHS The Michigan Department of Health and Human Services (MDHHS) is the oversight organization of all Medicaid programs for the State of Michigan, and as such, contracts with each of the waiver sites to manage, hire, or contract employees, and provide care to beneficiaries in the waiver program. As an oversight organization, MDHHS collects administrative, CQAR, and beneficiary data and has access to all current and past data of this nature. We will execute an IRB and DUA with MDHHS to perform this study.

Sites Home and Community Based Services Provider waiver program sites are under contract with State of MI MDHHS to manage, hire or contract employees, and provide care to beneficiaries in the waiver program. We will execute a contract and DUA with each site that agrees to participate to perform this study. Deployment will occur in a staged manner, with 2—4 sites each month until all are deployed.

CIM Center for Information Management (CIM) is under contract with MDHHS and 18 sites (20 years) to house and manage the EHR and billing software for the State of MI Medicaid waiver program. This platform contains beneficiary level data for all Medicaid beneficiaries in the waiver program where our study will occur.

The website (www.ciminc.com/) provides a description of CIM's mission and purpose; and contains a statement of HIPAA compliance, required by CMS and MDHSS. We will obtain a DUA. The following will occur.

1. De-identified data on beneficiaries outcomes from care by clinicians trained in CAPABLE at sites who do not opt-out will be obtained from CIM.
2. Data transfer to the university (PI/PM) will be electronic through a CIM data secure encrypted portal as the data will be de-identified.

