1.14 DATA ANALYSIS

Preliminary analysis

The distributions of outcomes, mediators, and potential covariates will be assessed, outliers will be investigated by inspecting the residuals, and models described below will be fit with and without outliers to examine their influence on the results. Analyses will be implemented in SAS 9.4 as follows:

Aim A1 To test the effects of MiCAP with IF alone versus MiCAP with IF+EF with respect to the site-level outcomes of adoption and sustainability (**primary**) and beneficiary-level outcomes of ADL/IADLs, pain, depression, falls, emergency department (ED) visits and hospitalizations (**secondary**) over the next 12 months. Primary outcomes will be analyzed using a linear mixed effects model with repeated measures: 11 monthly measures of the SIC, 11 monthly summary records of clinician's actions based on EHR documentation, and monthly for 9 months measures from IF tools (statistical model #1). Covariates will include trial arm, variables used in randomization (site's size and CQAR score), and time entered as a class variable to model potentially non-linear patterns. In addition, we will use general liner model to analyze clinicians' fidelity training data. Log-rank test and Cox proportional hazard modeling will be employed to analyze time spent in each stage (treated as censored if a site does not complete a given implementation stage). The test of significance of the coefficient of the trial arm variable will yield the formal test of hypothesis associated with this aim for the main (time-averaged) effect of IF+EF v. IF alone. The analysis of secondary beneficiary-level outcomes will employ use generalized linear model with appropriately distributed errors and the random effect of site added to account for nesting of individuals within sites. For counts of falls and health service use, Poisson error distribution will be specified. Alternatively, as a zero-inflated Poisson or negative Binomial model based on the distribution of the counts will be fit. The explanatory variables including trial arm will be evaluated as predictors of zero inflation (whether or not the count is zero), and as predictors of the magnitude of the count when it is not zero. Pre-intervention MDS assessment will be used to obtain baseline version of each outcome, which will be included as a covariate to explain the variation in post-intervention outcomes.

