Aim A2 Mechanism-of-action To determine whether the effects of EF+IF versus IF on primary outcomes are mediated by clinician attitude or self-efficacy at 9 months. In addition to statistical model #1, statistical model #2 will be fit at the clinician level with site as a random effect to account for nesting of clinicians within sites. To test for mediation, trial arm will be treated as the independent variable; each of the potential mediators (one at a time) will be tested for their effect on the outcome variable. We will use a bias corrected bootstrapping analytic strategy⁸⁶⁻⁸⁷ based on 5000 bootstrap samples to estimate confidence intervals around the indirect effect of the trial arm on the outcome variable, through the mediator. To establish mediation, the 95% confidence interval around the indirect must not include 0.

Aim A3 To benchmark the effects of IF and EF+IF on beneficiary outcomes following implementation as compared to pre-intervention. The analysis of this aim will use 2 repeated measures of beneficiary outcomes: at the start of this study (pre-intervention) and in the following 12 months. Time by trial arm interaction will be included. The least square (LS) means according to the interaction term will be output from this model, and differences from pre-to-post CAPABLE will be evaluated for each arm to gauge the magnitude and practical meaning of improvements.

Exploratory Aim A4 To compare the primary and secondary outcomes within 12 months, potential mediators at 9 months, and baseline leadership and readiness for sites with SIC of $>50\%$ versus sites with $SIC \leq 50\%$ at 6 months in each arm. General or generalized linear models (as appropriate based on outcome or potential mediator distribution) will include the binary indicator of whether SIC at 6 months is $>50\%$ or $<50\%$ in interaction with the trial arm variable. Differences between LS means according to SIC level will be tested within each arm. Because these analyses are exploratory, in addition to formal tests of significance, the effect sizes will be estimated.

Exploratory Aim A5 To explore whether baseline site leadership and readiness moderate the impact of EF+IF compared to IF on primary and secondary outcomes within 12 months in order to determine which sites may

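### Beneficiaries who join the Waiver after a site's month 0 have no entry limit, and the plan gives four different anchors for their baseline MDS

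*Combined protocol and SAP*

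**What the plan says.** **Who is included.** Section 1.7 defines the beneficiary sample as "beneficiaries who receive care from a clinician trained in CAPABLE". Section 1.18 covers current beneficiaries and also newcomers: "For new Waiver beneficiaries: sites will include Opt-out Consent document in enrollment packets", to be "hand delivered to the beneficiary during their initial home visit in the Mi Choice program". Neither section gives a last entry date, a minimum follow-up or a required baseline MDS.

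**Where baseline sits.** Four places describe it differently:
- Section 1.14, Aim A3: two measures, "at the start of this study (pre-intervention) and in the following 12 months".
- Section 1.13, data collection table: MDS from the EHR is listed at month 0 and month 12 only.
- Section 1.14, Aim A1: "Pre-intervention MDS assessment will be used to obtain baseline version of each outcome, which will be included as a covariate". No date is attached.
- Section 1.2: beneficiary data are the assessments before and after CAPABLE and those in between, which is a person-level anchor. Aim A3's own contrast is also worded as a change across CAPABLE.

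**Follow-up and calendar.** Aim A1 outcomes run "over the next 12 months" (section 1.3). Sites do not start together: "Deployment will occur in a staged manner, with 2—4 sites each month until all are deployed" (section 1.9). The count models in section 1.14 for falls and service use name Poisson, zero-inflated Poisson and negative binomial forms but no exposure offset.

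**The concern.** The sample can grow after a site has started, while two of the four baseline descriptions point to a date that later entrants have already missed. No rule says what happens to them. Two analysts could each follow the plan and build different cohorts with different baselines.

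Three things are at stake. First, the randomized exposure is the site's facilitation strategy. A cohort and a baseline covariate formed after that strategy has begun no longer have the full protection of randomization in Aim A1. Second, Aim A3 is a within-arm pre-post comparison without an untreated group. A person assessed on joining the program starts its 19 services (section 1.2) at about the same time as CAPABLE, and the change score cannot separate the two. Third, late entrants are observed for less than the 12 months over which outcomes are defined.

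**Working it through.** **1. Which anchors a later entrant can meet.** Take a beneficiary who joins in month 8 of the site's year.
- Study start (Aim A3): not possible, since the person was not yet in the program.
- Month 0 (schedule): not possible, for the same reason.
- Undated pre-intervention MDS (Aim A1): depends on which intervention is meant. It is not possible if this is the site's strategy. It is possible if it is the person's own CAPABLE start.
- Before CAPABLE (section 1.2): possible if an MDS is done before CAPABLE begins. The documents say only that the MDS is part of usual care (section 1.12) and give no intake assessment or interval.

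If the first measure is missing, the person is either dropped or contributes only to the post mean. In the second case the pre and post means describe different people. If a pre-CAPABLE MDS is used, it was taken after allocation and after the site's start.

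**2. Remaining follow-up.** A month-8 entrant has 12 − 8 = 4 months, or 4 × 52/12 = 17.3 weeks. CAPABLE is put at 20 weeks in section 1.2 and at 16 weeks in section 1.10, which also reports an extension to 32 weeks in the team's earlier adaptation. On either longer figure the course would not be finished by month 12. The durations need reconciling; no view is taken here on which applies.

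**3. Study start as a common date.** 18/4 = 4.5, so 5 monthly waves; 18/2 = 9 waves. The last wave starts 5 − 1 = 4 to 9 − 1 = 8 months after the first. If study start is one calendar date, it precedes deployment at the last sites by about that much.

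**4. Effect on precision.** Inputs from section 1.15: 9 sites per arm, 750 beneficiaries per site, ICC 0.01. Two-sided alpha 0.05 and 80% power are assumed, as neither is stated.
- Design effect = 1 + (750 − 1) × 0.01 = 8.49 (plan: 8.49).
- Effective n per arm = 9 × 750/8.49 = 795.05 (plan: 795).
- Detectable effect = (1.960 + 0.842) × √(2/795.05) = 0.1405 (plan: 0.14).

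The share without a usable month-0 baseline is not in the documents, so a range is assumed:
- 10% lost: effective n 784.9, detectable effect 0.1414.
- 30% lost: 757.2, 0.1440.
- 50% lost: design effect 1 + 374 × 0.01 = 4.74; n = 9 × 375/4.74 = 712.0; detectable effect 0.1485. Power at 0.14 falls from 79.7% to 75.2%.

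The number of sites and the ICC dominate, so restricting the cohort costs little. The average census is 15,000/18 = 833 per site, and 750/833 = 90%, so the month-0 roll is larger than the planned analysis sample.

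**5. Illustration of unequal exposure.** Turnover is not given. Suppose 20% of a steady 15,000 is replaced over a year, with entry and exit spread evenly. Then 3,000 enter, and 18,000 people are ever on the roll. Entrants average half a year, so they lack 3,000 × 0.5 = 1,500 person-years, or 1,500/18,000 = 8.3% of full exposure. Leavers lack as much again. At 10% and 30% turnover the entrants' part is 750/16,500 = 4.5% and 2,250/19,500 = 11.5%. In a month-0 cohort at 20% turnover the entrants' part disappears, but leavers still lack 1,500/15,000 = 10%. A cohort restriction alone therefore does not equalize exposure. All of this applies only if counts accumulate over follow-up.

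**The case against.** A reader might infer that new enrollees can have no baseline in any outcome model. The documents do not support that. Aim A1 attaches no date to its pre-intervention MDS, and section 1.2 accepts an assessment before the person's own CAPABLE start. The impossibility is confined to the Aim A3 wording and the month-0 schedule.

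Section 1.18 is also a consent provision and does not define an analysis cohort; intake throughout the study is inferred from the missing cut-off. Site-level clocks can reasonably be read into the plan: section 1.2 speaks of rolling enrollment, section 1.13 has data transferred when a site's period ends, and the schedule runs in numbered months. On that reading study start already means something close to site month 0.

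These points stand as limits, but they do not settle the matter. With site clocks, a person who joins after month 0 still lacks the Aim A3 first measure. With the person-level anchor, the baseline still follows allocation, and the other consequences for late entrants remain.

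It is also fair that an exposure shortfall of similar size in both arms would leave the Aim A1 rate ratio largely unchanged and mainly affect absolute rates. Differential entry by arm is a possibility that the documents do not demonstrate.

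**Conclusion.** The point holds as an inconsistency in the baseline anchor combined with open-ended entry. Late entrants cannot have the Aim A3 or month-0 measure. Using a pre-CAPABLE MDS instead gives a post-allocation baseline, an Aim A3 change that mixes Waiver entry with CAPABLE, and under 12 months of follow-up. Staged deployment makes a single study-start date unsuitable, by about 4 to 8 months for the last sites.

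The size of the bias cannot be stated. The documents give no turnover, MDS interval or recall window for falls, ED visits and hospitalizations, and do not say that an MDS is done at intake. A reader might infer from the turnover illustration that counts will be understated by some definite percentage, or that the arm comparison is biased in a known direction; neither follows.

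Nor is this a power problem: even a 50% loss takes the detectable effect only from 0.1405 to 0.1485. The affected outcomes are secondary, and section 1.15 attaches no hypothesis to Aim A3. The matter should be settled before the beneficiary data are analysed, but it does not touch the primary site-level outcomes.

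**What to change.** - In section 1.14, Aim A3, replace study start with each site's own month 0, define that date, and bring sections 1.2 and 1.13 and the Aim A1 text into line with it.
- For the main Aim A1 and A3 beneficiary analyses, use people on the site's roll at its month 0, with the last MDS on or before that date as baseline.
- Report later entrants separately, with their first MDS as baseline and time from entry stated.
- Where counts accumulate over follow-up, include observed time as an offset. This also covers beneficiaries who leave.

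The cost is wording plus a date filter on MDS data already requested for 2017-21 (section 1.8). The main analysis will have slightly fewer beneficiaries, and the baseline will be older for people who start CAPABLE well after month 0.

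The change does not remove selection through section 1.7's requirement of care from a CAPABLE-trained clinician. Facilitators encourage that training (section 1.11), so it could differ by arm. That is a separate issue and needs its own decision.

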1.19 PRIVACY AND CONFIDENTIALITY ISSUES

Any information about the individuals in the study, including identity and answers to questions are confidential and will not be shared with others. In addition, the responses will be combined with those of all others in the study. All study team members are Human Subjects and HIPAA trained and follow all privacy and confidentiality requirements.

1.20 STUDY WITHDRAWL OR DISCONTINUATION

A site, clinician, and/or a beneficiary may withdraw and/or discontinue their participation at any point in the project by notification of the internal facilitator and/or PI/PM via email, phone call, or in writing. Withdrawal and discontinuation are included in the contracts. Decisions to participate or not will not affect their current or future employment or status as a Medicaid program in the State. Three attempts at data collection will occur and if no response, no further contact will be attempted, and be considered a discontinuation.

1.21 POTENTIAL RISKS AND BENEFITS TO PARTICIPATION

Sites, clinicians and beneficiaries will be assured of the confidentiality of all information given and be protected in the following manner: 1) use of identification numbers rather than names with computerized data entry; 2) release of data in aggregate form only; and 3) omission of identifiers in all reports and presentations. Therefore, risk/benefit ratio is heavily weighted in favor of benefit for sites, and individual clinicians and beneficiaries.

Benefits of Participation

Sites There may or may not be direct benefits for the sites. Sites may gain knowledge from this study will help determine ways to assist waivers caring for disabled individuals living in the community, may improve retention of clinicians, and may save costs. Findings may help future waiver sites, clinicians, and beneficiaries.

Clinicians There may or may not be direct benefits for the clinicians. Clinicians will not be placed at increased physical, financial, or legal risk as a result of taking part in this study. Clinicians will learn new knowledge and skills that may or may not benefit ability to perform their duties when employed as a clinician. It may take some time and effort for clinicians to complete the training and to answer questions.

Beneficiaries There may or may not be direct benefits for the beneficiaries. Beneficiaries may experience improvement in activities of daily living, instrumental activities of daily living, pain, falls, depression, hospital

and ED visits. Beneficiaries will not be placed at increased physical, financial, or legal risk as a result of taking part in the study. It may take some time and effort for beneficiaries to answer questions and adapt to the extra home visits. Beneficiaries will continue to receive care under the direction of their waiver clinicians, even if the beneficiaries choose not to take part in this study.

Protection against Study Risks

Sites can agree or not agree to participate in the study. A contract will be obtained prior to data collection.

Clinicians Clinicians can agree or not agree to participate in the study. Clinicians (RNs/OTs/SWs/IFs) employed by the sites will participate in this study. A consent will be obtained from a clinician prior to completing surveys. Clinicians will be informed that completing a survey is voluntary and their responses will be kept confidential. Any report of this research will not include their name or any other information by which they could be identified. For those clinicians who consent and complete CAPABLE training: The IF who is also a supervisor at the site where the clinician is employed and performs "usual" Waiver care will have access to "all" beneficiary electronic health records, and be informed of CAPABLE trained fidelity performance/non-performance by a clinician and/or be informed by PI/PM of need for a clinicians to have remediation for fidelity to CAPABLE. To minimize the risk, IFs will be trained in how to motivate and conduct remediation. Will include in the contract with sites that need for clinician remediation would not impact a clinicians employee status if consent to participate in the study.

Beneficiaries Beneficiaries have the option to opt out of the study if desired; and will receive "usual" waiver care regardless of decision to participate or not participate in the study.

Protecting Confidentiality Identifying information (name, address, date of birth, Social Security or Medicare numbers) are not used to identify those who participate in the study. Those who participate will be assigned an identification number which will become the identifier of records for all who participate. This number will be given to study personnel to enter into the study database. Only the PI/PM will link the identification number with the data to the central location for review.

